### Primary objective:

- To reduce the recurrence rate of patients with a first episode of CDI hospitalized during the period of intervention by increasing the compliance with clinical practice guidelines (appropriate length and choice of drug for CDI specific treatment according to the severity of the initial episode) and by a close follow-up during the period of higher risk, avoiding factors that are known to predispose to recurrence.

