## **Study Subjects:**

### Inclusion criteria:

- Patients diagnosed with a first episode of CDI in the University Hospital “12 de Octubre”, Madrid, Spain, requiring hospitalization or emergency room admission longer than 48 hours, from the beginning of the study on (1-February-2017).
- Patient or his/her representative sign the informed consent

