**Leukocyte count to consider severity of the CDI:** Any white blood cell count (WBC) measured between two days before and two days following the date of the stool sample. If a patient had WBC measured on the date of the stool sample then this was selected. If they did not have WBC measured on the date of the stool sample but had WBC measured between one day before and one day following their stool sample, then this was selected. If they did not have WBC measured between one day before and one day following their stool sample but had WBC measured between two days before and two days following their stool sample, then this was selected. If they did not have WBC measured on the date of the stool sample but had WBC measured both one day before and one day following the date of stool sample, or had WBC measured both two days before and two days after the stool sample but not between these measurements, then the highest of the two measurements was selected.

**Definition of treatment response:** Treatment response is present when either stool frequency decreases or stool consistency improves and parameters of disease severity (clinical, laboratory, radiological) improve and no new signs of severe disease develop.

**Definition of recurrent CDI:** Recurrence is present when CDI re-occurs within 8 weeks of successfully completing treatment for CDI.

**Duration of diarrhea:** was the sum of days from day 1 to the last day with diarrhea, followed by 2 or more days without diarrhea.

**Antibiotics of high, medium and low risk for CDI:** according to the table proposed by Aldeyab et al (S3. J Antimicrob Chemother 2012; 67: 2988–2996).

**Table S3.** Risk classification of antibiotics

High risk	Medium risk	Low risk
Second-generation cephalosporins [J01DC; cefaclor, cefuroxime].	Combinations of penicillins including $\beta$ -lactamase inhibitors [J01CR; amoxicillin/clavulanic acid]	Combinations of penicillins including $\beta$ -lactamase inhibitors [J01CR; piperacillin/tazobactam] Penicillins with extended spectrum [J01CA; amoxicillin, ampicillin; pivmecillinam] $\beta$ -Lactamase-sensitive penicillins [J01CE; phenoxymethylpenicillin, benzylpenicillin]

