### **Statistical Plans**

We present an exploratory study which aim is to evaluate the impact of an intervention, consisting on a bundle of measures for patients diagnosed with a first episode of CDI. The bundle includes antimicrobial stewardship, close follow-up, optimization of specific treatment for CDI and potential search for clinical and biological markers of recurrence. The required sample size was estimated under the hypothesis that the application of a strategy based on a bundle to improve the management of CDI, would decrease the risk of recurrence as compared to the usual care performed in the retrospective period.

A recent review that evaluated the frequency of treatment failure and recurrence of CDI showed a recurrence rate after metronidazole treatment of 27.6% in studies performed in Europe during the previous 10 years.

Based in the previous literature, we expected a cumulative incidence of recurrence in the control group of 27.6%. The study would require a sample size of 99 for each group (i.e. a total sample size of 198, assuming equal group sizes), to achieve a power of 80% for detecting a reduction in proportions of 0.15 between the two groups (reference group - intervention) at a two sided p-value of 0.05.

1. Vardakas KZ, Polyzos KA, Patouni K, Rafailidis PI, Samonis G, Falagas ME. Treatment failure and recurrence of *Clostridium difficile* infection following

treatment with vancomycin or metronidazole: a systematic review of the evidence. *Int J Antimicrob Agents* 2012; 40:1–8.

2. Ralph B. D'Agostino, Sr, Sylva H. Collins, Karol M. Pencina, Yin Kean, and Sherwood Gorbach. Risk Estimation for Recurrent *Clostridium difficile* Infection Based on Clinical Factors. *Clinical Infectious Diseases* 2014 58: 1386-1393.

The data of qualitative variables will be expressed as absolute values and relative frequencies. The data of quantitative variables will be shown as mean  $\pm$  standard deviation should be demonstrated normal distribution or median with interquartile range otherwise. Categorical variables will be compared using  $\chi^2$  or Fisher's exact test for paired samples. Continuous variables will be compared using the Student's t-test or the Mann-Whitney U test for paired samples.

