The impact of our intervention will be analyzed as a categorical variable and will be entered as a predictor variable into a conditional logistic regression model, adjusted by potential confounding factors. Associations will be given as relative risks.

A set of sensitivity analyses will be explored by restricting the overall cohort according to the type of episode (first episode versus recurrence) and by hospital ward (medical versus surgical).

Statistical analysis will be conducted using SPSS version 22.0 (SPSS Inc, Chicago, Illinois, USA).

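### Two independent-sample tests are labelled as paired, and the first-episode-versus-recurrence restriction cannot check the primary effect at patient level (minor)

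*Combined protocol and SAP*

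**What the plan says.** The Statistical Plans section compares categorical variables by chi-square or Fisher's "exact test for paired samples", and continuous variables by Student's t or the "Mann-Whitney U test for paired samples". No McNemar or Wilcoxon signed-rank test is named anywhere.

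Under Patients selection and follow-up, historical controls are matched to prospective patients on severity of the first episode and on the Charlson Age-Comorbidity Index (CACI). The main analysis respects this: the intervention "will be entered as a predictor variable into a conditional logistic regression model, adjusted by potential confounding factors". The sample-size text works "assuming equal group sizes", but the matching ratio and the conditional strata are not stated.

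The sensitivity analyses follow directly after the main model. They consist of "restricting the overall cohort according to the type of episode (first episode versus recurrence) and by hospital ward (medical versus surgical". No unit of analysis and no outcome is given. The inclusion criteria admit "Patients diagnosed with a first episode of CDI in the University Hospital", the comparison group is also limited to first episodes, and the primary objective is "To reduce the recurrence rate of patients with a first episode of CDI hospitalized during the period of intervention".

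**The concern.** **(a) Test names.** Fisher's exact and Mann-Whitney U have no paired form under those names, so an analyst must discard either the name or the word paired. The matching and the conditional model show that paired analysis was intended, so the names are what is wrong. Student's t has a valid paired form, and chi-square is ambiguous because it may mean McNemar. If the tests are run as named between periods, the univariate p-values ignore the matching. For continuous variables these tests are the only comparison the plan names, because the conditional logistic model takes a binary outcome. Duration of diarrhoea, which "was the sum of days from day 1 to the last day with diarrhea", is an example, although no objective lists it.

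**(b) Restriction.** Everyone enters with a first episode, and recurrence is the primary outcome. Splitting patients by first episode versus recurrence is therefore either no restriction or a selection on the outcome. A result from it could be reported as a robustness check when it is uninformative or selected.

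**Working it through.** **Inputs.** From Statistical Plans: 99 per group, 27.6% recurrence in controls, absolute reduction 0.15 (so 12.6%), two-sided 0.05. The within-pair correlation phi is not in the documents; 0 to 0.3 is assumed.

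**The plan's own figure.** The pooled two-sided formula gives n = [1.960·√(2·0.201·0.799) + 0.842·√(0.276·0.724 + 0.126·0.874)]² / 0.15² = 111 per group, not 99. Power at 99 is about 75%. That is a separate matter; 99 serves here only as the number of pairs.

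**(a) Binary variable, 1:1 pairs.** Joint probability p11 = p1·p2 + phi·√(p1·q1·p2·q2). At phi = 0.1 this is 0.0348 + 0.1·0.1483 = 0.0496, so the discordant cells are 0.276 − 0.0496 = 0.2264 and 0.126 − 0.0496 = 0.0764. Summing the exact probabilities of all 171,700 paired tables in which each test rejects gives:

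| phi | Type I error, unpaired chi-square | Power, unpaired chi-square | Power, McNemar | Power, Fisher | Power, exact McNemar |
|---|---|---|---|---|---|
| 0 | 0.0512 | 0.766 | 0.760 | 0.703 | 0.692 |
| 0.05 | 0.0455 | 0.771 | 0.783 | 0.707 | 0.714 |
| 0.1 | 0.0400 | 0.778 | 0.806 | 0.713 | 0.737 |
| 0.2 | 0.0295 | 0.791 | 0.853 | 0.724 | 0.789 |
| 0.3 | 0.0200 | 0.807 | 0.899 | 0.737 | 0.846 |

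Type I error is for 27.6% in both periods; power is for 27.6% against 12.6%. Chi-square minus McNemar runs from +0.6 to −9.2 points, and Fisher minus exact McNemar from +1.1 to −10.9. The smallest expected cell is 19.9, so chi-square is the relevant choice for the primary outcome. Fisher would be used for sparse variables: at 4% in both periods and phi 0 to 0.2, its type I error falls from 1.7% to 0.8%, against 1.7% to 1.3% for exact McNemar.

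*How large can phi be?* If correlation comes only from matching on severity and CACI, the SD of recurrence risk between strata must be √(phi·0.201·0.799), which is 9.0, 12.7, 17.9 and 21.9 points for phi 0.05, 0.1, 0.2 and 0.3. Against a mean risk of 20.1%, the upper values are demanding, so phi up to about 0.1 and a loss of 0 to 3 points is more plausible.

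*Continuous variable* (assumed normal, 0.4 SD shift, correlation 0 to 0.3, 20,000 simulations per setting): Mann-Whitney power goes from 78.0% to 82.4%, signed-rank from 77.6% to 90.5%. Mann-Whitney type I error falls from 5.0% to 2.0%.

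**(b) Restriction, patient level.** First-episode subset: all patients, so it repeats the main analysis. Recurrence subset: the recurrence proportion is 100% in both periods, so no effect on it can be estimated.

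**(b) Restriction, episode level.** Recurrers at planning rates: 99·0.276 = 27.3 and 99·0.126 = 12.5. With an assumed control risk p of second recurrence, exact unpaired chi-square power is:

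| p | Subset, 27 vs 12: p vs p/2 | All enrolled: 0.276p vs 0.063p | All enrolled, no effect after first recurrence: 0.276p vs 0.126p |
|---|---|---|---|
| 20% | 5% | 37% | 16% |
| 30% | 14% | 54% | 25% |
| 40% | 22% | 69% | 35% |
| 50% | 32% | 81% | 43% |

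The last column shows that the all-enrolled comparison includes the effect on first recurrence.

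*Selection.* Take two equal risk groups at 27.6% ± 12 points, with second-recurrence risks of 20% and 60% that the bundle does not change. Controls in the subset: (15.6·0.2 + 39.6·0.6)/55.2 = 48.7%. If the bundle removes 15 points from each group: (0.6·0.2 + 24.6·0.6)/25.2 = 59.0%, a spurious 10 points against the bundle. This is a boundary case, since low-risk recurrence falls to 0.6%. With ± 5 points and risks of 30% and 50% the figure is 2 points; with a constant risk ratio it is 0.

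**The case against.** The strongest reply is that this is a wording slip in a study declared exploratory. The paired intention is explicit, and the main estimate comes from a model that respects the matching. That stands, and it is why the point is minor.

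A simple swap to McNemar and signed-rank would also be wrong in places. Those tests need 1:1 pairs, which the plan implies but does not state. Ordinary McNemar does not handle variables with more than two categories, such as severity or antibiotic risk class. Comparing recurrers with non-recurrers for the marker objective is not a matched comparison, so independent-sample tests are right there. All of this stands and shapes the fix.

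On the restriction, the plan does not say that it tests the primary effect, and an episode-level reading is coherent: the secondary objectives address later recurrences, follow-up continues through them, and prescription appropriateness is rated episode by episode. This too stands, so the patient-level criticism does not dispose of every use of the split. It does not supply the missing unit and outcome, or remove the selection.

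A reader might infer that the misnamed tests invalidate the primary result or inflate false positives. The documents do not support this: the primary model is conditional, and with zero or positive correlation the error is neutral or conservative. A reader might also infer that the ward restriction breaks matched pairs. That depends on 1:1 strata and on ward shares that the plan does not give, so it is not shown to be an error.

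**Conclusion.** Minor, but wrong as written.

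(a) Fisher's exact and Mann-Whitney U are misnamed. The consequence is confined to univariate between-period comparisons and is conservative: for phi 0 to 0.3, about 0 to 9 points of power for a binary variable tested by chi-square (up to about 11 for Fisher against its exact paired counterpart), with 0 to 3 more plausible. This assumes 1:1 pairs, planning rates, non-negative correlation, and that chi-square is run in its unpaired form. At zero correlation nothing is lost.

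(b) At patient level the episode-type restriction cannot check the primary effect; that follows from the entry criteria and the primary objective and needs no assumption. At episode level it compares about 27 with 12 patients chosen by a post-enrolment event that the bundle aims to prevent. Power is low, and the direction and size of any bias depend on how the bundle acts across risk groups, with zero possible.

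Neither part changes the main estimate.

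**What to change.** **(a)** State the matching ratio and the conditional strata, then name tests for between-period comparisons:

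- If matching is 1:1: McNemar for binary variables (exact if discordant pairs are few); Stuart-Maxwell (marginal homogeneity) or Bowker (symmetry) for more than two categories; paired t or Wilcoxon signed-rank for continuous variables.
- If strata are severity-by-CACI sets: stratified tests, namely Cochran-Mantel-Haenszel for categorical and van Elteren for continuous variables.
- Keep independent-sample tests for comparisons that are not between matched patients, such as recurrers against non-recurrers.

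**(b)** Do not present the episode-type restriction as a sensitivity analysis of the primary effect. Compare second and further recurrences between periods with all enrolled patients as the denominator, and say that this includes the effect on first recurrence and does not isolate better treatment of recurrences. If an episode-level analysis is kept, for example prescription appropriateness by episode type, state its unit and outcome, allow for repeated episodes within a patient, and label it descriptive.

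The cost is SAP wording and minor analysis work on the same data.

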## **MATERIAL AND METHODS:**

**Study Design:** Exploratory, interventional before-after prospective, quasi-experimental study comparing the baseline phase (2015) with the interventional phase (2017)

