## **Patients selection and follow-up:**

The first 100 patients fulfilling the inclusion criteria will be included in the prospective phase of the study. Patients will be identified by means of daily report of the positive results from the Microbiology lab. They will be prospectively followed 8 weeks after the end of treatment for the episode of CDI. If there are one or more recurrences, the follow-up will endure until 8 weeks after the end of the last CDI treatment.

They will be retrospectively compared with patients diagnosed with a first episode of CDI during the previous year (2015) in which there was not a systematical intervention by a member of the Infectious Diseases Unit.

To ensure comparability, patients from the retrospective period will be chosen and matched with patients included in the prospective period according to the severity of the initial episode of CDI and to the Charlson Age-Comorbidity Index (CACI).

If patients diagnosed during 2015 are not enough to fulfil those comparison criteria, we will search backwards through patients diagnosed with a first episode of CDI during 2014 to be matched.

The retrospective follow-up will also endure until 8 weeks after the end of the last CDI treatment.

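### The only adjusted model estimates an odds ratio, but the plan reports its result as a relative risk, and recurrence is too common for the two to agree

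*Combined protocol and SAP*

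**What the plan says.** The Statistical Plans section gives one regression model for the effect of the bundle and, in the sentence that follows it, the reporting scale. The intervention is a predictor in a "conditional logistic regression model, adjusted by potential confounding factors. Associations will be given as relative risks". Nothing in the documents connects the two, whether a log-binomial or modified Poisson model, standardisation, an odds-ratio-to-relative-risk conversion, or a statement that the odds ratio is meant as an approximation.

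Three other parts of the plan bear on the point.

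- The sample size rests on a common outcome: "we expected a cumulative incidence of recurrence in the control group of 27.6" (per cent), with power calculated "for detecting a reduction in proportions of 0.15 between the two groups".
- Comparison patients come from an earlier period and are matched to the prospective patients on severity of the first episode and on the Charlson Age-Comorbidity Index (Patients selection and follow-up).
- Crude results will be available: "The data of qualitative variables will be expressed as absolute values and relative frequencies".

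The design is described as an "Exploratory, interventional before-after prospective, quasi-experimental study".

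**The concern.** The exponentiated coefficient from a conditional logistic regression is an odds ratio within matched sets. It is close to a relative risk only when the outcome is rare, and recurrence at 27.6% is not rare. For any effect other than none, the odds ratio lies further from 1 than the relative risk, so mislabelling always exaggerates the effect.

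The design does not rescue the label. Comparison patients are chosen by calendar period and baseline matching. They are not sampled by outcome or from risk sets, so the odds ratio does not become a risk ratio through sampling.

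The model cannot supply the conversion either. The conditional likelihood removes the matched-set intercepts, so the fit gives no baseline risk from which to derive a relative risk.

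At stake is the size of the effect that readers take away. In a non-randomised before-after comparison the regression-adjusted estimate is the one they are likely to rely on, and the plan has only one.

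**Working it through.** **Inputs.** From Statistical Plans: control risk p0 = 0.276; absolute reduction 0.15, so bundle risk p1 = 0.276 − 0.15 = 0.126; 99 patients per group. The plan states no odds ratio or relative risk to reproduce. The figure of 99 is used below only for scale. It does not itself follow from the stated two-sided inputs (the usual pooled formula gives 111 per group), but that is a separate matter and nothing here depends on it.

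**Step 1: the two measures at the design rates.**

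- RR = p1/p0 = 0.126/0.276 = 0.457, a 54% relative reduction.
- OR = [p1/(1−p1)]/[p0/(1−p0)] = (0.126/0.874)/(0.276/0.724) = 0.378, which would be read as 62%.
- The odds ratio misread as a relative risk implies a bundle risk of 0.276 × 0.3782 = 0.104. That is 10.4% instead of 12.6%, or a reduction of 17.2 points instead of 15.0.

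**Step 2: other rates.** The first two rows below keep the control risk and shrink the effect. The last two keep the 0.15 reduction and use the ends of the 20 to 30% recurrence range given in Background and Rationale.

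| Control | Bundle | RR | OR |
|---|---|---|---|
| 27.6% | 17.6% | 0.638 | 0.560 |
| 27.6% | 22.6% | 0.819 | 0.766 |
| 20% | 5% | 0.250 | 0.211 |
| 30% | 15% | 0.500 | 0.412 |

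Read as percentage reductions, the first two rows are 36% against 44% and 18% against 23%.

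**Step 3: what the conditional model targets.** With 1:1 pairs and no covariates, the conditional odds ratio is the ratio of the two kinds of discordant pair. If outcomes within a pair were independent, this is (0.126 × 0.724)/(0.276 × 0.874) = 0.0912/0.2412 = 0.378, the odds ratio from Step 1. If pairs differ in underlying risk, the conditional odds ratio moves further from 1 at the same marginal risks. The documents give no figure for that variation. Assuming normally distributed pair effects on the logit scale:

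| Assumed SD | Conditional OR |
|---|---|
| 0 | 0.378 |
| 0.5 | 0.364 |
| 1 | 0.327 |
| 1.5 | 0.278 |
| 2 | 0.229 |

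The marginal relative risk stays at 0.457 throughout.

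**Step 4: scale against imprecision** (unpaired, unadjusted, 99 per group).

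- SE(log RR) = √[0.724/(99×0.276) + 0.874/(99×0.126)] = 0.311; 95% CI 0.25 to 0.84.
- SE(log OR) = √[1/(99×0.276) + 1/(99×0.724) + 1/(99×0.126) + 1/(99×0.874)] = 0.377; 95% CI 0.18 to 0.79.
- Shift = ln(0.4565/0.3782) = 0.188, which is 0.188/0.311 = 0.61 of the first SE and 0.188/0.377 = 0.50 of the second.

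**The case against.** The plan names a model and then a scale; it never says that exponentiated coefficients will be labelled relative risks. On this view the step between the two is merely missing, and the overstatement is possible rather than certain. The powered contrast is a difference in proportions, which is unaffected. Because the cohort is matched on exposure, the crude ratio of the two recurrence proportions is a valid risk ratio already controlled for severity and comorbidity, as far as the matching succeeds, and readers would see it beside any mislabelled estimate. The study is exploratory, the shift is within one standard error, and one changed phrase repairs the text.

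Much of this stands. The harm in the report does depend on how the sentence is applied, the test of no effect is untouched, and the crude risk ratio is a useful safeguard. The 62% against 54% contrast is illustrative, since the planned conditional, adjusted odds ratio cannot be computed from the documents.

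It does not remove the fault. Following the two sentences as they stand, with no intermediate step named, produces a mislabelled estimate. The crude ratio handles only the two matching factors, not the other confounders for which the regression is planned. Wide confidence intervals do not excuse a wrong label: a larger sample would shrink the standard error but not this discrepancy.

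**Conclusion.** The concern holds. The stated model and the stated measure do not match, and the outcome is too common for one to stand in for the other. At the plan's own rates the odds ratio overstates the relative reduction by about 8 percentage points (62% against 54%), and by less for smaller effects. That size assumes the design rates and ignores pairing and adjustment; with risk varying between pairs the gap would be larger. The error affects the reported size of the effect, not its direction or the test of no effect, and it is smaller than the sampling error. It should be corrected before analysis, because it concerns the study's only regression-adjusted estimate of the bundle's effect.

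**What to change.** Either of two changes resolves the inconsistency.

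1. **Relabel.** State that associations from the conditional logistic model will be given as odds ratios with 95% confidence intervals. This is a wording change and is sufficient by itself.
2. **Estimate relative risks directly.** Replace or supplement the model with a modified Poisson regression (log link, robust variance clustered on the matched pair). It should include severity of the initial episode and the Charlson Age-Comorbidity Index as well as the other confounders, because clustering on the pair corrects only the variance.

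Option 2 adds one model on data already collected. It has two downsides: the ratio will look less favourable than the odds ratio, and the expected events are few (99 × 0.276 + 99 × 0.126 = 27.3 + 12.5, about 40 recurrences), so the list of other confounders must be short and named in advance.

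A risk difference with a 95% confidence interval would be a useful addition, since the sample size is framed on that scale, but it is not needed to correct the error.

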### Secondary objectives:

- To reduce the rate of second and further recurrences by increasing the compliance with clinical practice guidelines (appropriate length and choice of drug for the treatment of first and further recurrences).
- To discontinue or to reduce the spectrum of unnecessary antibiotic treatments in this population ("antimicrobial stewardship"), especially during the episode of CDI and during the following 8 weeks.
- To discontinue inappropriate treatment of asymptomatic patients colonized by *Clostridium difficile*.
- To identify clinical and biological markers that could be used as predictors of recurrence.
- To identify patients with a high number of recurrences, that could benefit from novel or experimental treatments.

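### The planned restriction to recurrent episodes cannot support a comparison of the two periods: the subset is empty, all events, or selected on the primary outcome

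*Combined protocol and SAP*

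**What the plan says.** Statistical Plans describes sensitivity analyses "restricting the overall cohort according to the type of episode (first episode versus recurrence" and, separately, by ward; the ward restriction is not at issue here. The model in the same section is a "conditional logistic regression model, adjusted by potential confounding factors". The section does not say what the outcome is within the episode-type restriction, whether the rows are patients or episodes, or what happens to matched pairs.

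The rest of the protocol fixes who is in the cohort and what is measured:

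- **Inclusion criteria** (intervention period): "Patients diagnosed with a first episode of CDI in the University Hospital".
- **Patients selection and follow-up** (control period): "They will be retrospectively compared with patients diagnosed with a first episode of CDI during the previous year (2015". If 2015 does not supply enough matches, first episodes from 2014 are used.
- **Matching** (same section): "according to the severity of the initial episode of CDI and to the Charlson Age-Comorbidity Index (CACI".
- **Primary objective**: "To reduce the recurrence rate of patients with a first episode of CDI hospitalized during the period of intervention".
- **Definitions**: a recurrence is a new CDI episode in the eight weeks after successful treatment, so it can only arise after baseline.
- **Secondary objectives**: fewer second and later recurrences, to be reached through "appropriate length and choice of drug for the treatment of first and further recurrences".
- **Follow-up after a recurrence** is extended in the prospective group, and for controls: "The retrospective follow-up will also endure until 8 weeks after the end of the last CDI treatment".

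**The concern.** A sensitivity analysis by subset should split the cohort on something fixed before the intervention could act. Here nobody enters at a recurrence, and recurrence is the event the bundle is designed to prevent. The restriction therefore splits the cohort on its own outcome, or does not split it at all.

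The practical risk lies with the secondary objective on second and later recurrences. Statistical Plans gives no other analysis dedicated to it, so a reader would naturally look in the recurrence subset. A difference between periods there, or its absence, could be taken as the bundle's effect on the treatment of recurrences. It would in fact mix that effect with any difference in who still recurs under the bundle, and it would be very imprecise.

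**Working it through.** **Inputs.** From Statistical Plans: control recurrence 27.6%, planned absolute reduction 0.15 (so 12.6% under the bundle), 99 per group, 80% power, two-sided 0.05. From Patients selection and follow-up: 100 prospective patients. The documents give no risk of a second recurrence; it is assumed to be 20% to 50%.

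**The plan's own figure.** The plan gives no size for the recurrence subset. Its sample size, by the pooled normal formula, is

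n = [1.96 × sqrt(2 × 0.201 × 0.799) + 0.842 × sqrt(0.276 × 0.724 + 0.126 × 0.874)]² / 0.15² = 111 per group.

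The stated 99 is not reproduced (power at 99 is 75.4%). That is a separate matter, and nothing below depends on it.

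**Reading 1: split by index episode.** Recurrence subset: 0 patients in each period. First-episode subset: the whole cohort, so it repeats the main analysis.

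**Reading 2: patients who recurred, outcome still first recurrence.** All are events. In any pair where both members have the event, the conditional likelihood contribution is exp(b)/exp(b) = 1 for every b. No period effect can be estimated.

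**Reading 3: patients who recurred, later outcome** (second recurrence, or appropriateness of treatment of the recurrence).

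*Subset size per 100 enrolled:* 27.6 control v 12.6 intervention.

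*Intact matched pairs.* Both members must recur:

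- independence within pairs: 99 × 0.276 × 0.126 = 3.4 pairs;
- assumed within-pair correlation 0.2: 99 × [0.276 × 0.126 + 0.2 × sqrt(0.276 × 0.724 × 0.126 × 0.874)] = 6.4 pairs;
- ceiling: 99 × 0.126 = 12.5 pairs.

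Only discordant intact pairs inform the conditional model. At assumed second-recurrence risks of 40% v 20%, 3.4 pairs yield 3.4 × (0.4 × 0.8 + 0.2 × 0.6) = 1.5 discordant pairs.

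*Unpaired precision.* Half-width = 1.96 × sqrt[r(1 − r)(1/27.6 + 1/12.6)]:

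| Assumed second-recurrence risk r | 95% CI half-width |
|---|---|
| 20% | 26.7 points |
| 30% | 30.5 points |
| 50% | 33.3 points |

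*Selection.* Suppose the bundle causes no recurrences and detection is equal in both periods. Of 27.6 control recurrences, 15 have no counterpart under the bundle: 15/27.6 = 54%. Let d be the difference in second-recurrence risk between patients who still recur and those whose recurrence is prevented. With no effect on second recurrence, the subset would still show a difference of 0.543 × d. At an assumed d of ±20 points this is ±10.9 points; at d = 0 it is 0. The documents give no value or sign for d.

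**Alternative: all enrolled patients, outcome two or more recurrences.** With risks 0.276r and 0.126r and 100 per group, half-width = 1.96 × sqrt{[0.276r(1 − 0.276r) + 0.126r(1 − 0.126r)]/100}. This is 5.4 points at r = 0.2, 6.6 at r = 0.3 and 8.3 at r = 0.5.

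The result is a total effect. At r = 0.3 in both periods it is 8.3 − 3.8 = 4.5 per 100, all from preventing first recurrences. If the bundle also cut r to 0.2, it would be 8.28 − 2.52 = 5.8. Of that, 15 × 0.3 = 4.5 is prevention and 12.6 × 0.1 = 1.3 (22%) is treatment of recurrences.

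**The case against.** The best defence is that the plan leaves the restriction undefined and that a sensible use exists. The Definitions judge appropriateness of prescribing for each episode, and the bundle ties treatment to whether there were earlier episodes. Showing first and recurrent episodes separately for that process measure is natural. This stands as a case for description. It does not rescue a between-period test, because which recurrent episodes exist in the intervention period depends on the bundle. Matching on initial severity and comorbidity, and adjustment for confounders, may reduce that selection but cannot be assumed to remove it.

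Three further objections stand and limit the point. The all-events result requires first recurrence to remain the outcome, which the text does not say. The ±27 to ±33 interval is for an unpaired comparison that is not the planned model; it serves only to show that setting the pairing aside does not help. And the selection bias rests wholly on an assumed d, with no estimate at all for appropriateness of treatment.

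A reader might infer that the subset is known to be biased for or against the bundle. The documents do not support that: if the bundle prevents recurrences in the same proportion in high-risk and low-risk patients, this selection produces no difference.

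**Conclusion.** The concern holds. With first-episode enrolment in both periods and recurrence as the primary outcome, the recurrence subset is empty, consists only of events, or is selected on what the bundle is meant to change. In the last case the planned conditional model would rest on about 3.4 of 99 pairs (independence assumed; at most 12.5). An unpaired comparison of about 28 v 13 patients per 100 would be uncertain by ±27 to ±33 points (assumed second-recurrence risk 20% to 50%). The selection bias has unknown size and direction and may be zero.

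Two stronger inferences should be resisted. One is that the primary comparison is compromised: it uses all enrolled patients and is not touched by this defect. The other is that the index-episode comparison is therefore sound: this point does not examine its other sources of bias and makes no such claim.

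The weight is minor, since this is a sensitivity analysis in a study that the protocol itself calls exploratory.

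**What to change.** In Statistical Plans:

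1. Drop the between-period test in the recurrence subset. The first-episode restriction needs no separate analysis, since it is the main analysis.
2. For the secondary objective on later recurrences, compare two or more recurrences (yes/no), or the number of recurrences per patient, over all enrolled patients in both periods. Label the result as the total effect of the bundle, including prevention of the first recurrence.
3. Report recurrent episodes and the appropriateness of their treatment by period descriptively, and state that differences are not to be read as a bundle effect.

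This changes wording only: follow-up past a recurrence is already planned in both periods. The price is that no test isolates the effect of better treatment of recurrences. The total effect is also imprecise (about ±5 to ±8 points), and at r = 0.3 its interval of ±6.6 exceeds the 4.5-point difference. It also depends on recurrences being detected equally well in both periods. The bundle offers telephone and email contact to pick up relapses early, while control data come from medical records, so that limitation should be stated with the result.
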